15.2. Determination of Sample Size

To reasonably characterize the PK of OCA in patients with hepatic impairment, a simulation-based approach estimated a requirement of approximately 20 patients in the OCA treatment group assuming a 15% discontinuation rate. A total of 30 patients is adequate with 10 patients on placebo to be included as a comparator and 20 patients on OCA. An additional 20 patients will be enrolled to support safety and efficacy evaluations. Therefore, approximately 50 patients (including at least 20% of patients with CP-C) will be randomized in a 1:1 ratio to 1 of the 2 treatment groups: Placebo and OCA.

15.3. Pharmacokinetic Analyses

The PK Population will be used for analysis of PK parameters, which include plasma OCA (parent) and its conjugates (glyco-OCA and tauro-OCA), total OCA, metabolite OCA glucuronide, and potentially other conjugates or metabolites not yet identified.

PK analysis will be based on the PK population. Values will be calculated using non-compartmental methods. The values will be summarized by active treatment group using descriptive statistics. Full details regarding the planned analyses, methods, and outputs for the study will be detailed in the statistical analysis plan (SAP).

15.4. Safety Analyses

Safety analyses will be conducted using the Safety population. Safety data, including AEs, AEs of special interest including pruritus and hepatic safety, vital signs, ECG, and clinical laboratory results will be summarized by treatment group using the Safety Population.

The incidence of TEAEs and SAEs will be tabulated by system organ class (SOC) and preferred term (PT) for each treatment group, and similarly by severity and relationship to treatment.

Laboratory parameters, physical examinations including vital signs, and ECGs will be summarized by treatment group using descriptive statistics at Baseline and at each scheduled post-Baseline visit. The absolute change from baseline will also be summarized.

No inferential comparison with formal statistical hypothesis testing will be performed for safety endpoints.

15.4.1. Adverse Events

AEs will be coded using Medical Dictionary for Regulatory Activities (MedDRA). Summary tables of TEAEs will be provided.

Each AE summary will be displayed by treatment group. Summaries that are displayed by SOC and PT will be ordered by descending order of incidence of SOC and PT within each system organ class. Summaries of the following types will be presented:

- Overall summary of TEAEs.
- Patient incidence of TEAEs and the total number of entries by MedDRA SOC and PT. This summary will be repeated for all subgroups.
- Patient incidence of TEAEs by MedDRA SOC, PT, and highest severity. At each level of patient summarization, a patient is classified according to the highest severity if the patient reported 1 or more events. AEs with missing severity will be considered severe for this summary.
- Patient incidence of TEAEs by MedDRA SOC, PT, and closest relationship to investigational product (Related/Not Related). Related AEs are those with relationships reported as “Definite,” “Probable,” or “Possible,” and unrelated AEs are those with relationships reported as “Unlikely” or “Not Related.” At each level of patient summarization, a patient is classified according to the closest relationship if the patient reported 1 or more events. AEs with a missing relationship will be considered related for this summary.
- Patient incidence of serious TEAEs and the total number of entries by MedDRA SOC and PT.
- Patient incidence of TEAEs leading to investigational product withdrawal or study discontinuation by MedDRA SOC and PT. This is a subset of the AEs where Action Taken with Study Treatment is checked as “Drug Withdrawn” or where “Patient Discontinued from Study” is checked.

The following listings will be presented by treatment group and patient:

- All adverse events.
- Serious adverse events (This is a subset of the AEs where serious is marked as “Yes”).
- Severe adverse events (This is a subset of AEs where severity is marked as “Severe”).
- Related adverse events (This is a subset of the AEs where relationship marked as “Definite,” “Probable,” or “Possible”).

- Adverse events leading to Study Drug Withdrawal or Study Discontinuation (This is a subset of the AEs where Action Taken with Study Treatment is checked as “Drug Withdrawn” or where “Patient Discontinued from Study” is checked).
- Adverse events leading to death (This is a subset of the AEs where the corresponding AE number is specified on the Death eCRF).

Adverse events of special interest as defined in [Section 13.1.1.4](#) will be summarized for each treatment group.

15.4.2. Clinical Laboratory Evaluations

Laboratory parameters will be summarized in standard international (SI) system of units by treatment group using descriptive statistics at Baseline and at each on-study evaluation. Re-test or unscheduled results will not be summarized but will be included in the data listings. The change from Baseline will also be summarized. Baseline is defined as the mean of all available evaluations prior to treatment.

In addition, shift tables (ie, low-normal-high at Baseline versus low-normal-high at post Baseline visit in a 3-by-3 contingency table) from Baseline to worst value, last value, and at each scheduled post-Baseline visit will be provided for hematology and serum chemistry by treatment group to assess changes in laboratory values from Baseline to each on-study evaluation.

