7.4.2. Liver Biochemistry Assessments for Potential Hepatic Injury or Hepatic Decompensation

[figure not shown]
Liver biochemistry will be assessed to evaluate biochemical triggers that will prompt an immediate reevaluation of patients for potential hepatic injury or hepatic decompensation. These assessments will be performed at:

- Each protocol-specified visit (Table 1)
- Unscheduled visits as needed in the event of signs or symptoms of suspected hepatic injury or decompensation or if laboratory alerts have been triggered

It is important that the laboratory assessments be completed as required and that the central laboratory be used for assessments whenever possible. In the event that a patient cannot return to the clinic for a scheduled or unscheduled visit, or there is an event that triggers a need for an immediate assessment, the use of a local lab is permissible at the discretion of the Investigator. In these cases, the Investigator will obtain the laboratory results and the laboratory normal ranges.

The process for assessing criteria is presented in Figure 2, and the specific threshold(s) for each laboratory analyte to trigger mandatory repeat testing and, potentially, a complete patient evaluation (depending on the repeat result) are summarized in Table 3.

Figure 2: DILI Management Algorithm

DILI = drug-induced liver injury; IP = Investigational Product

NOTE Other laboratory criteria include: ALT, AST, total bilirubin, INR, and electrolytes (sodium).

Table 3: Liver Laboratory Criteria for Monitoring of Suspected Hepatic Injury or Potential Hepatic Decompensation and Criteria for Interruption or Discontinuation of Investigational Product

A. Laboratory Criteria for Monitoring Suspected Hepatic Injury		
Laboratory Parameter	Action Taken	Rechallenging Criteria
Total Bilirubin		If a patient interrupts IP, they may be rechallenged after a minimum of 30 days if fully resolved OR stable and approved by the Medical Monitor and Investigator.
Baseline \leq ULN and \geq 3x baseline	Interrupt IP	
Baseline $>$ ULN and \geq 2x Baseline	Interrupt IP	
ALT or AST		
$>$ 3x baseline (and $>$ ULN)	Interrupt IP	
\geq 2x baseline	Repeat Test in 2 to 3 days, interrupt IP if still elevated	
Electrolytes^a		
Sodium $<$ 130 mEq/L	Repeat Test in 2 to 3 days, interrupt IP if still below limit	
B. Laboratory Criteria for Monitoring Potential Hepatic Decompensation (Absence of Clinical Symptoms)		

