15. STATISTICAL METHODS AND ANALYSES

Individual patient data obtained from electronic case report forms (eCRFs), central laboratories, external sources, and any derived data will be presented in data listings by patient. All data listings that contain an evaluation date will contain a relative study day. Pre-treatment and on treatment study days are numbered relative to the day of the first dose of investigational product which is designated as Day 1.

All output will be incorporated into Microsoft Word rich text format (.rtf) files, sorted and labeled according to the International Conference on Harmonisation (ICH) recommendations, and formatted to the appropriate page size(s).

Tabulations will be produced for appropriate demographic, Baseline, efficacy, and safety parameters.

For categorical variables, summary tabulations of the number and percentage of patients within each category (with a category for missing data) of the parameter will be presented. Percentage calculations will be based on non-missing data, unless otherwise specified. Percentages are rounded to 1 decimal place, unless otherwise specified.

For continuous variables, the number of patients, mean, standard deviation (SD), standard error of the mean (SEM), median, minimum, and maximum values will be presented. The precision of summary statistics, unless otherwise specified will be as follows: mean and median to 1 more decimal place than the raw data, and SD and SEM to 2 decimal places more than the raw data. In general, the decimal places should not exceed 3 decimal places unless appropriate. Confidence intervals (CIs) will be provided and will be rounded to 1 decimal place, unless otherwise specified.

Time-to-event data will be summarized using Kaplan-Meier (KM) methodology using 25th, 50th (median), and 75th percentiles with associated 2-sided 95% CIs, as well as percentage of censored observations.

There will be no formal hypothesis testing in this study. However, summary statistics for each treatment group will be presented, as well as 95% CIs for the difference between the treatment groups.

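### The laboratory safety tables in Section 15.4.2 are insensitive to hepatic injury: repeat and unscheduled results are left out, the shift grid stops at high, and INR has no shift table

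*Protocol*

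**What the plan says.** Section 15.4.2 summarizes laboratory parameters "by treatment group using descriptive statistics at Baseline and at each on-study evaluation", with change from Baseline. It then sets a rule: "Re-test or unscheduled results will not be summarized but will be included in the data listings". A second paragraph adds shift tables laid out as "low-normal-high at Baseline versus low-normal-high at post Baseline visit in a 3-by-3 contingency table", which run "from Baseline to worst value, last value, and at each scheduled post-Baseline visit will be provided for hematology and serum chemistry by treatment group".

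Table 11 in Section 13.2.6 places bilirubin, ALT, AST and sodium under serum chemistry. INR stands in a separate coagulation row.

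Section 7.4.2 describes how suspected hepatic injury is followed up. Biochemistry is assessed at scheduled visits and also at unscheduled ones. For ALT or AST at 2x baseline or more, Table 3 says "Repeat Test in 2 to 3 days, interrupt IP if still elevated", and sodium below 130 mEq/L is handled in the same way. If the patient cannot attend or an immediate test is needed, "the use of a local lab is permissible at the discretion of the Investigator". Section 7.6 adds further repeat testing during close observation.

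**The concern.** Comparing safety with placebo is one of the two primary objectives (Section 6.1). The patients are Child-Pugh B or C, many results will be abnormal at entry, and Table 3 sets its triggers mainly as multiples of baseline or increments over it. The values that describe a hepatic event as it unfolds are mostly repeat or unscheduled draws, and these go to listings.

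The shift tables are the only laboratory output in Section 15.4.2 that counts patients by arm. If they leave out those draws, and cannot register worsening above ULN, the reader gets no by-arm count of the biochemical events that the protocol itself treats as signals.

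**Working it through.** The plan states no figure to reproduce. The check is a reading of the text with two illustrations.

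**1. Which records feed the worst value.** The exclusion rule names no exception. The worst-value shift is a summary, so read literally it uses scheduled draws only. The shift sentence attaches the word scheduled only to its third item, so a reader could take worst value and last value to include everything. On that reading the two sentences conflict. Either way the source of the worst value needs stating.

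**2. What the grid can show.** Set ULN = 1 and let b be baseline bilirubin. The Table 3 Part A trigger is 3b if b is at or below 1, and 2b if b is above 1.

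| Baseline (xULN) | Value at trigger (xULN) | Shift cell |
|---|---|---|
| 0.5 | 3 x 0.5 = 1.5 | normal to high |
| 0.9 | 3 x 0.9 = 2.7 | normal to high |
| 1.1 | 2 x 1.1 = 2.2 | high to high |
| 2 | 2 x 2 = 4 | high to high |
| 5 | 2 x 5 = 10 | high to high |

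Every patient with baseline above ULN stays on the diagonal, however large the rise. ALT and AST above 3x baseline behave the same way.

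**3. INR.** Table 3 Part B has triggers at a rise above 0.3 and at a value of 2.0 or more. Shift tables cover hematology and serum chemistry, so INR has none.

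**4. Do other outputs fill the gap?**
- The by-visit summaries include coagulation and show extremes (Section 15: "median, minimum, and maximum values will be presented"), but they use scheduled draws and do not count patients past a threshold.
- The ANCOVA in Section 15.5 covers INR, bilirubin, ALT and AST at Week 48. Section 15.7 imputes nothing, so a patient without a Week 48 value does not contribute.
- MELD shifts end in one category of 15 or more, while entry allows MELD up to 24.
- Child-Pugh gives bilirubin its full 3 points above 3.0 mg/dL (Table 12), so a rise from 4 to 8 mg/dL changes nothing there.
- The adverse events of special interest in Section 13.1.1.4 are decompensation events. They include a persistent 3-point MELD rise but no ALT, AST or bilirubin threshold.
- Section 15.9 has a committee adjudicate suspected drug-related hepatic injury. Section 15.4 names no table of its findings.

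**5. Chance that an excursion meets a scheduled draw.** Table 1 draws safety laboratories at Weeks 3, 6, 12, 18, 24, 30, 36, 42 and 48, then every 3 months (about 13 weeks). For an excursion of d weeks starting at random, with draws g weeks apart, P = d/g, capped at 1. Durations are assumed.

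| d (weeks) | g = 6 | g = 13 | Simulation on the actual visits to Week 48 |
|---|---|---|---|
| 1 | 1/6 = 17% | 1/13 = 8% | 17% |
| 2 | 2/6 = 33% | 2/13 = 15% | 35% |
| 3 | 3/6 = 50% | 3/13 = 23% | 53% |
| 4 | 4/6 = 67% | 4/13 = 31% | 68% |
| 6 | 6/6 = 100% | 6/13 = 46% | 100% |

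The simulation is slightly higher because of the extra Week 3 draw. Overlap means that some part of the excursion is sampled, not that its peak is.

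**The case against.** Keeping unscheduled draws out of by-visit means is sound practice, because symptom-driven tests would distort them. The rule applies equally to both blinded arms, every excluded value remains in the listings, and at about 25 patients per arm (50/2) those listings can be read patient by patient. The safety analysis is descriptive, with no formal test. All of this stands.

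Three stronger inferences are tempting, and the documents do not support them.

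- **That the plan cannot show hepatic injury, or omits INR.** INR is missing only from the shift tables. It is in the descriptive summaries and the ANCOVA, and it enters MELD. Adverse events of special interest, serious events, events leading to withdrawal, MELD and Child-Pugh shifts and adjudication all show some injury.
- **That most peaks are lost.** This holds only for short excursions and random timing. A repeat test often follows an abnormal scheduled value, which is summarized. The highest triggers (bilirubin at 2x or 3x baseline, ALT or AST above 3x) act on the first observation, which may itself be a scheduled draw.
- **That the comparison is biased toward no difference.** That would require excursions to be more frequent or more severe on OCA, which nothing here establishes.

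The source records for a worst value might also be left to the SAP. Here, however, the protocol fixes an exclusion, and an SAP that used all results would depart from its literal text.

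**Conclusion.** The point holds as a weakness of tabulation. Section 15.4.2, read literally, keeps repeat and unscheduled results out of the worst-value shift. Its grid cannot register worsening above ULN, and INR has no shift table. No stated table counts patients per arm who meet the Table 3 thresholds.

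The share of excursions missed is not a property of the documents. At nominal 6-week spacing it runs from about 83% for an assumed 1-week excursion (100 - 17) to 50% for 3 weeks and none at 6 weeks or more. In the extension the gaps are wider. The insensitivity of the grid needs no such assumption: it applies to every patient whose baseline is above ULN.

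This is a cheap improvement and not a must-fix.

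**What to change.** In Section 15.4.2, or in the SAP with a matching correction to that section:

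- Keep by-visit summaries on scheduled draws.
- State that worst post-baseline values use all results: scheduled, repeat, unscheduled and local laboratory. Local values should be standardised to that laboratory's reference range, which Section 7.4.2 already has the investigator obtain.
- Add one table counting patients per arm who meet each existing Table 3 threshold for ALT/AST, bilirubin, INR and sodium, with Table 3's own exceptions for anticoagulants and vitamin K deficiency.
- Add INR to the shift tables.
- Report the number of tests per arm beside the worst values.

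The cost is a sentence or two and one extra table, using data already collected. The downside is that more unscheduled testing in one arm can raise its worst values, which is why the test counts are needed. No clinical rule changes.

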15.4.3. Additional Safety Analysis

Vital Signs and Weight

The results and change from Baseline to each on-study evaluation visit will be summarized by treatment group for weight, oral temperature, sitting heart rate, respiratory rate and sitting blood pressure.

Electrocardiograms

Electrocardiogram (ECG) results will be summarized at each on-study visit descriptively, including the number and percentage of patients with normal, abnormal not clinically significant, and abnormal clinically significant results at Baseline and each on-study evaluation.

15.4.4. Adverse Events of Special Interest

Pruritus: Treatment-emergent pruritus, defined as any PT including “Prur,” will be summarized separately by the MedDRA SOC, treatment group, and PT as a subset of all TEAEs. This summary will be repeated for patients with “new or worsened” pruritus events, as defined as follows:

- Mild, moderate, or severe treatment-emergent pruritus events in patients with no pruritus at Baseline, or
- Worsening of the severity of the Baseline condition in patients with pruritus at Baseline.

Baseline pruritus is defined as the Investigator’s rating of severity as collected on the PBC Disease History eCRF. Patients whose Baseline severity is severe will be counted as worsening if an AE of pruritus with severe is recorded.

An analysis of treatment-emergent pruritus event days per patient years on study will be performed. The days at each severity grade, including the total days of event, the total patient years on study, and the event days per patient year on study at each severity grade, including the total, will be summarized. Each individual patient year on study will be derived as the last known date during the study minus the first dose date plus 1 divided by 365.25 days/year.

In order to explore the relationship between pruritus and the investigational product, the following time-to-event analyses will be performed:

- Time to first onset of treatment-emergent pruritus
 - The time to the start of the first episode will be calculated by date of onset of first episode – date of first dose of investigational product + 1.
 - Patients who never reported an AE of pruritus will be censored at the date of last contact.
- Time to onset of the first moderate or severe treatment-emergent pruritus
 - The time to the start of the first moderate or severe pruritus will be calculated by date of onset of the first moderate or severe pruritus – date of first dose of investigational product +1.
 - Patients who never reported a moderate or severe AE of pruritus will be censored at the date of completion or discontinuation.
- Time to onset of the first severe treatment-emergent pruritus
 - The time to the start of the first severe pruritus will be calculated by date of onset of the first severe pruritus – date of first dose of investigational product +1.
 - Patients who never reported a severe AE of pruritus will be censored at the date of completion or discontinuation.

The analysis of time to first onset of treatment-emergent pruritus AE, time to onset of the first moderate or severe treatment-emergent pruritus, and onset of the first severe treatment-emergent pruritus will include the number of patients with pruritus (first onset, first moderate or severe, first severe), the number of patients without pruritus (censored), and the minimum and maximum times in days. KM estimates will be calculated by treatment group. The tabulation will include the KM estimate methodology using 25th, 50th (median), and 75th percentiles of the medians and corresponding with associated 2-sided 95% confidence intervals (CIs), if the medians can be estimated as well as percentage of censored observations.

Fatigue: Treatment-emergent fatigue is defined as any PT which includes “Fatigue.” New or worsened treatment-emergent fatigue is defined as follows:

- Any mild, moderate, or severe treatment-emergent fatigue events in patients with no fatigue at Baseline, or
- Worsening of the severity of the Baseline condition in patients with fatigue at Baseline.

Baseline fatigue is defined as the Investigator's rating of severity as collected on the PBC Disease History eCRF. Patients whose Baseline severity is severe will be counted as worsening if an AE of fatigue with severe is recorded.

An analysis of treatment-emergent fatigue event days per patient years on study will be performed. The days at each severity grade, including the total days of event, the total patient years on study, and the event days per patient year on study at each severity grade, including the total, will be summarized. Each individual patient year on study will be derived as the last known date during the study minus the first dose date plus 1 divided by 365.25 days/year.

In order to explore the relationship between fatigue and the investigational product, the following time-to-event analyses will be performed:

- Time to first onset of treatment-emergent fatigue
 - The time to the start of the first episode will be calculated by date of onset of first episode – date of first dose of investigational product + 1.
 - Patients who never reported an AE of fatigue will be censored at the date of last contact.
- Time to onset of the first moderate or severe treatment-emergent fatigue
 - The time to the start of the first moderate or severe fatigue will be calculated by date of onset of the first moderate or severe fatigue – date of first dose of investigational product +1.
 - Patients who never reported a moderate or severe AE of fatigue will be censored at the date of last contact.
- Time to onset of the first severe treatment-emergent fatigue
 - The time to the start of the first severe fatigue will be calculated by date of onset of the first severe fatigue – date of first dose of investigational product +1.
 - Patients who never reported a severe AE of fatigue will be censored at the data of last contact.

The analysis of time to first onset of treatment-emergent fatigue AE, time to onset of the first moderate or severe treatment-emergent fatigue, and onset of the first severe treatment-emergent fatigue will include the number of patients with pruritus (first onset, first moderate or severe, first severe), the number of patients without fatigue (censored), and the minimum and maximum times in days. KM estimates will be calculated by treatment group. The quartiles, including the median time-to-event and their respective 2-sided 95% CIs, will be presented. KM estimates will be plotted as a “survival curve” for each treatment group.

